# 4.3 Non-clinical Safety, Toxicity and Pharmacokinetics

The evidence from the comprehensive analytical characterisation and comparability program performed using state of the art technology and orthogonal methods to compare structural and functional attributes has shown that MB05 drug product is similar to US- and EU-Synagis® in terms of primary structure, higher order structure and confirmational stability, post-

translational modifications (including charge variants and glycosylation profile), purity and biological properties.

The presence of trehalose in the formulation of MB05 (not present in US- or EU-Synagis®) is not expected to impact the clinical pharmacokinetic (PK) profile.

Detailed information is available in the MB05 IB.

## 4.4 Clinical Experience

This is a first-in-human study of the Synagis® biosimilar MB05. The reference product Synagis® was first approved by the US Food and Drug Administration (FDA) in 1998 and by the European Medicines agency (EMA) in 1999.

As a proposed biosimilar, the clinical experience with Synagis® (as described in the Synagis® summary of product characteristics) (most recent versions) is deemed applicable to MB05.

## 4.5 Rationale and Considerations for Proposed Clinical Use

MB05 is being developed as a potential biosimilar to Synagis® for all indications for which Synagis® is approved.

This study is designed to demonstrate PK similarity of the proposed biosimilar test product MB05 and the reference products EU- and US-Synagis®.

## 4.6 Justification for Dose Level

A single weight-adjusted dose of 3 mg/kg has been selected for this study to support PK and safety comparisons between MB05, EU- Synagis® and US- Synagis®. Publicly available data shows that palivizumab has linear PK relationship up to 15 mg/kg (Groothuis and Nishida, 2002). Based on this, the PK of palivizumab allows extrapolation from the 3 mg/kg intramuscular (IM) dose to the 15 mg/kg dose IM while minimising the risk for healthy volunteers and reducing the injection volume.

### 4.7 Risk Assessment and Guidance for Investigators

MB05 is an investigational drug. As with any investigational drug, unexpected clinically significant or serious adverse events (SAEs) may occur with the use of MB05. All participants treated with MB05 should be closely monitored by means of adverse events (AEs), vital signs, physical examinations, electrocardiogram (ECGs), and clinical laboratory tests.

As with any IM injection, palivizumab should be given with caution to patients with thrombocytopenia or any coagulation disorder. Accordingly, appropriate provisions have been made in the study eligibility criteria, and healthy volunteers must have adequate coagulation and bone marrow function at screening and prior to first dose, as determined by screening clinical laboratory safety blood tests.

Identified risks for MB05 are based on safety issues highlighted in the product labelling for palivizumab in sections "Warnings and Precautions" / "Special Warnings and Precautions for Use" and/or the "Adverse Reactions / Undesirable Effects".

mAbxience Research SL

Based on data from clinical studies and post-marketing data for Synagis®, the most serious adverse reactions are anaphylaxis and other acute hypersensitivity reactions. Accordingly, participants will remain under the supervision of clinic staff for at least 24 hours following dose administration. Vital signs and other safety assessments will be performed at regular intervals during this time. Other adverse reactions occurring with Synagis® (reported in clinic studies and post-marketing reports in paediatric patients) include:

*Very common* ( $\geq 1$  *in* 10):

- Rash
- Pyrexia

Common ( $\geq 1$  to 10 in 100):

- Injection site reaction
- Apnoea

Uncommon ( $\geq 1/1,000$  to < 1/100):

- Thrombocytopenia
- Convulsion
- Urticaria

The Warnings and Precautions sections of the Synagis® product information and the Synagis summary of product characteristics (latest versions) should be consulted for detailed recommendations on the identification, monitoring, and management of the risks that are associated with Synagis® and are likely to be associated with MB05.

Further information regarding MB05 is available in the IB.

## 5 STUDY OBJECTIVES

### 5.1 Primary

The primary objective of this study is to establish the bioequivalence between MB05 and EU-Synagis®, between MB05 and US-Synagis® and between EU-Synagis® and US-Synagis® up to Day 99, in terms of:

- Area under the serum concentration versus time curve from time zero to infinity (AUC0-inf)
- Maximum observed serum concentration (Cmax)

#### 5.2 Secondary

The secondary objectives of this study are to:

- 1. Compare the PK of MB05 with EU- Synagis® and US-Synagis® following a single 3 mg/kg IM injection in healthy adult volunteers.
- 2. To assess the safety and tolerability of MB05, EU- Synagis® and US-Synagis®
- 3. To assess the immunogenicity of MB05, EU-Synagis® and US-Synagis®

## 6 STUDY DESIGN AND ENDPOINTS

## 6.1 Overall Design Summary

This is a multicentre, randomised, double-blind, 3-arm parallel group study. Up to a total of 141 participants are planned to be enrolled and randomised to receive a single dose of MB05, EU-Synagis® or US-Synagis with participants randomised to Arm A, B or C in equal proportions (1:1:1) as shown in Table 1. Randomisation will be stratified based on the subject's body weight (50 to <75 kg and  $\geq$ 75 to 95 kg) and gender (male and female). To achieve balance, the number of subjects enrolled in each stratum should be a multiple of 3, where possible.

Participants will be enrolled across multiple sites in Australia and New Zealand.

In Group 1, a total of 9 participants will be enrolled and dosed with MB05, EU-Synagis® or US-Synagis® (1:1:1). Once all participants in Group 1 have completed the Day 8 visit, a safety review committee (SRC) will meet to review all available safety data from Group 1, up to and including Day 8. No additional enrolment or dosing of the remaining participants should occur until the safety review is complete.

Following approval by the SRC, Group 2 may be enrolled (n=132, randomised 1:1:1 MB05: EU-Synagis®: US-Synagis®).

	Arm A	Arm B	Arm C	Total number			
	MB05	EU-Synagis®	US-Synagis®	of participants			
Group 1	3	3	3	9			
SRC review of Group 1							
Group 2	44	44	44	132			
				141			

### 6.2 Detailed Description of Study Design

The study schedule and procedures are identical for each group. Healthy volunteers will be screened between Day -28 and Day -2. Eligible participants will be admitted to the clinical facility the day prior to dosing (Day -1).

On Day 1, participants will be randomised to receive a single IM dose of 3 mg/kg MB05, EU-Synagis® or US-Synagis®. Participants will remain in the clinical site until all post-dose assessments have been completed on Day 2. If any participants experience any clinically significant AEs during the confinement period, they may remain at the clinical site for further observation at the discretion of the Principal Investigator (PI).

Participants will return to the clinical site on Days 3, 4, 5, 6, 8, 15 ( $\pm$  1 day), 22 ( $\pm$  1 day), 29 ( $\pm$  1 day), 36 ( $\pm$  1 day), 43 ( $\pm$  1 day), 57 ( $\pm$  3 days), 71 ( $\pm$  3 days) and 85 ( $\pm$  3 days) for follow-up assessments. The end of study (EOS) visit will be on Day 99 ( $\pm$  3 days). Safety assessments (including safety laboratory blood and urinalysis sampling, vital signs assessments, body

weight determination ECG assessments, physical examination, and injection site reaction assessments) will be performed as indicated in the schedule of assessments (APPENDIX 1).

Additional blood samples will be collected for PK evaluations at each scheduled visit. Blood samples for analysis of anti-drug antibody (ADA), neutralising antibody (nAb). (Figure 1 and APPENDIX 1).

## Figure 1. Summary of Key Procedures

Abbreviations: ADA = anti-drug antibody; IM = intramuscular; nAb = neutralising antibody; PK = pharmacokinetic; SRC = safety review committee. Notes: ...X.... indicates multiple samples collected.

Dosing will occur in a sequential manner. The decision to proceed to Group 2 group will be based on review of available blinded safety data from Group 1, up to and including Day 8, by the SRC.

At a minimum, the SRC will consist of the PI(s) who have enrolled participants, an independent medical monitor (IMM) and the Sponsor medical representative (SMR), however all Investigators involved in the study will be invited to attend the meeting, regardless of whether they have enrolled participants into Group 1. Other individuals (e.g., medical experts) may also be invited to participate and provide additional input into the review process, if required.

Following review of the data, the SRC will discuss the findings and recommend proceeding to Group 2 or terminating enrolment. There is no formal requirement for an SRC meeting in Group 2. Safety and tolerability will be reviewed in an ongoing manner during this part of the study.

# 6.3 Dose Stopping Rules

The decision to proceed to Group 2 will be made following evaluation of safety data from Group 1, up to and including Day 8 (i.e., clinical laboratory blood and urinalysis results, vital signs assessment, ECG assessments, physical examination findings and AE data) by the SRC. The clinical facility will provide the SRC with blinded safety data during the study.

Dosing will proceed until evaluation of all subjects has been completed or the trial is stopped by the SRC. Temporary suspension of further dosing may be decided by the SRC if any of the following criteria are fulfilled:

• One occurrence of an SAE assessed to be at least possibly related to the study drug and

that in the opinion of the SRC has a high likelihood to repeat in additional groups and would mean a significant risk to study participants

- Multiple occurrences of Hy's law criteria are met, as defined by at least 3-fold. elevations of serum alanine aminotransferase (ALT) or aspartate aminotransferase (AST) above the upper limit of normal (ULN), plus an elevation of serum total bilirubin > 2 times ULN without elevated serum alkaline phosphatase (ALP), and no other disease or condition can be found to explain the liver test abnormalities, and no other potential explanation in the opinion of the SRC can be a probable cause for this event, and in the opinion of the SRC study continuation would mean a significant risk to study participants
- If 2 or more participants experience the same or similar Grade III or higher AE which is possibly or probably related to the study drug, and according to SRC opinion study continuation would mean a significant risk to study participants
- Presence of any effects that are assessed as probably related to study drug that are, in the opinion of the SRC, medically relevant and may potentially endanger the welfare of study participants.

For any of the scenarios described above, the SRC will review all available safety data and will recommend if the group or the entire study should be terminated. No more healthy volunteers should be enrolled (or participants dosed) until this safety review is completed.

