## 12 ASSESSMENT AND MANAGEMENT OF ADVERSE EVENTS

## **12.1 Adverse Event Definition**

An **AE** is any untoward medical occurrence in a patient or clinical investigation participant administered a pharmaceutical product and which does not necessarily have a causal relationship with this treatment. An AE can therefore be any unfavourable and unintended sign (including an abnormal finding), symptom, or disease temporally associated with the use of a medicinal (investigational or non-investigational) product, whether or not related to that medicinal (investigational or non-investigational) product (based on International Council for Harmonisation [ICH] definition)

Any AE where a causal relationship with the study treatment is at least a reasonable possibility (i.e., possibly/probably or definitely related), is referred to as an **Adverse Drug Reaction**.

An **SAE** is any AE that, at any dose:

- Results in death.
- Is life-threatening (The term 'life-threatening' in the definition of 'serious' refers to an event/reaction in which the participant was at risk of death at the time of the event/reaction; it does not refer to an event/reaction which hypothetically might have caused death, if it were more severe).
- Requires inpatient hospitalisation or prolongation of an existing hospitalisation (only hospitalisations that are longer than expected based on Investigator judgement, will be considered prolonged hospitalisations).
- Results in persistent or significant disability/incapacity (an AE that results in a substantial disruption of a person's ability to conduct normal life functions).
- Is a congenital anomaly/birth defect (A congenital anomaly/birth defect that occurs in the offspring of a participant exposed to the study treatment).

Medical and scientific judgement should be exercised in deciding whether other situations should be considered serious, such as important medical events that may not be immediately life-threatening or result in death or hospitalisation but might jeopardise the participant or might require medical or surgical intervention to prevent one of the other outcomes listed in the above definition. These should also be considered serious. Examples of such events are intensive treatment in an emergency room or at home for allergic bronchospasm, blood dyscrasias or convulsions that do not result in hospitalisation, or development of drug dependency or drug abuse.

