# 12.2.2 Assessment of Causality

The Investigator will make an assessment as to the relationship between a study treatment and the occurrence of each AE/SAE. The Investigator will use clinical judgement to determine whether or not the AE/SAE is causally related to the study treatment(s). Alternative causes, such as natural history of an underlying medical condition, concomitant therapy, other risk factors, and the temporal relationship of the event to the study treatment will be considered and investigated. The Investigator will also consult the IB (or the product information sheet in instances where the study treatment is an approved agent) in the determination of his/her assessment.

The causal relationship of the study treatment to an AE will be rated according to the following 5-point scale (Table 6):

Causal Relationship	Definition
Unrelated	Clearly and incontrovertibly due only to extraneous causes, and does not meet criteria listed under unlikely, possible or probable.
Unlikely	Does not follow a reasonable temporal sequence from administration; may have been produced by the participant's clinical state or by environmental factors or other therapies administered.
Possibly	Follows a reasonable temporal sequence from administration of the study treatment; may have been produced by the participant's clinical state or by environmental factors or other therapies administered.
Probably	Clear temporal association with improvement on cessation of study treatment. Reappears upon rechallenge if rechallenge occurs) or follows a known pattern of response to the study treatment.
Definitely	Cannot be reasonably explained by an alternative explanation, e.g., concomitant drug(s), concomitant disease(s). The relationship in time is very suggestive.

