### 14.1 Adverse Events

AE verbatim terms will be coded using the version 25.0 of the Medical Dictionary for Regulatory Activities (MedDRA). AEs and SAEs are defined in the study protocol.

- Treatment Emergent Adverse Events (TEAEs) are defined as adverse events that occurred or worsened from the first administration of study drug. If determination cannot be made as to whether the event is treatment emergent due to missing or incomplete data, the adverse event will be treated as treatment emergent.
- Treatment-Related are defined as any TEAEs reported with the causality of "Possibly", "Probably", "Definitely" to study treatment.

All AE summaries will be restricted to TEAEs only.

The TEAE summaries will include:

- Overall Summary of TEAEs
  - o TEAEs
  - Treatment Related TEAEs
  - Serious TEAEs
  - Serious Treatment Related TEAEs
  - TEAEs leading to death
  - TEAEs leading to study withdrawal

The following table summaries will be presented by SOC and PT by treatment groups defined in Section 4.6:

- TEAE summary by SOC and PT
- TEAE summary by SOC, PT and Severity
- TEAE summary by SOC, PT and relationship (study treatment)
- Serious TEAE summary by SOC and PT
- Treatment Related TEAE summary by SOC and PT
- Serious Treatment-Related TEAE summary by SOC and PT
- Treatment Related TEAE summary by SOC, PT and Severity
- TEAE summary if events leading to study withdrawal by SOC and PT

The above items will be presented using summary tables, which will include the number of participants (%) experiencing an event and the number of events and the number of events. If a Participant experienced the same adverse event multiple times, this will only be counted once for the purpose of counting the number of Participants experiencing that adverse event. Summary tables will be done for the Safety Analysis Set for treatment groups defined in Section 4.6. Where SOC and PT are reported, the display will be sorted by the descending order by SOC and then by PT in the Overall treatment group.

All AEs will be listed and will include the verbatim term, SOC, PT, SAE, start/end date/time, causality/severity, relationship to study treatment, relationship to procedure of injection, outcome, action taken, and study withdrawal. A separate listing will be created for SAEs. These listings will be presented by treatment groups (Section 4.6) sorted by Participant ID and AE start date for the Safety Analysis Set, along with age, sex, race, and baseline weight of the Participant.

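### Two stopping criteria in protocol section 6.3 omit Definitely, the strongest rating on the protocol's own causality scale

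*Protocol*

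**What the plan says.** Section 6.3 of the protocol lists four circumstances in which the safety review committee (SRC) may temporarily suspend dosing. Three of them use a causality rating:

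- Criterion 1, serious events: "One occurrence of an SAE assessed to be at least possibly related to the study drug".
- Criterion 3, two or more participants with the same or a similar "Grade III or higher AE which is possibly or probably related to the study drug".
- Criterion 4: "Presence of any effects that are assessed as probably related to study drug", where the SRC also judges the effect medically relevant and potentially dangerous.

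Criterion 2, Hy's law cases, does not use the causality scale. The section then attaches a consequence to the list: "For any of the scenarios described above, the SRC will review all available safety data", and enrolment and dosing are held until that review is finished.

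The scale is set in section 12.2.2: "The causal relationship of the study treatment to an AE will be rated according to the following 5-point scale". Its levels (Table 6) are Unrelated, Unlikely, Possibly, Probably and Definitely, each with its own definition.

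**The concern.** A stopping rule should not become harder to meet as the evidence of causality grows stronger. Criteria 3 and 4 name individual levels of the scale and stop one short of the top. Neither has the words at least, which make criterion 1 open-ended.

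The written review and hold follow only from the listed scenarios. An event outside the list can be stopped for, but nothing in section 6.3 requires a review or a pause. This matters most after the Day 8 review of Group 1. Group 2 holds 132 of the 141 planned participants, and for that stage the protocol says: "There is no formal requirement for an SRC meeting in Group 2". An ad-hoc meeting is possible under section 12.8, but it depends on an Investigator's request in consultation with the sponsor. Section 4.4 describes this as the first study of MB05 in humans, and it runs at several sites in healthy volunteers, so the rule should read the same way to everyone.

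**Working it through.** The plan gives no figure to reproduce. The check compares the wording of each rule with the scale.

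**Step 1. Levels covered on a literal reading**

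| Place | Possibly | Probably | Definitely |
|---|---|---|---|
| Section 6.3, criterion 1 (SAE) | yes | yes | yes |
| Section 6.3, criterion 3 (Grade III or higher) | yes | yes | **no** |
| Section 6.3, criterion 4 (any effect) | no | yes | **no** |
| Section 12.1, adverse drug reaction ("i.e., possibly/probably or definitely related") | yes | yes | yes |
| SAP 14.1, treatment-related ("Treatment-Related are defined as any TEAEs reported with the causality of" all three levels) | yes | yes | yes |

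The other two definitions of a related event, and the first criterion in the same list, all include Definitely. Neither document gives a reason for leaving it out of criteria 3 and 4.

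**Step 2. Does another criterion catch these events?** Criterion 1 needs a serious event. Section 12.2.1 says that severity and seriousness are different things, so a Grade III event can be non-serious. Criterion 2 needs the Hy's law pattern. A non-serious Grade III event outside Hy's law therefore depends on criteria 3 and 4.

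**Step 3. Rating combinations.** Take two participants with the same event of this kind, each rated at one of the three related levels. The number of unordered pairs is 3 × 4 / 2 = 6.

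| Pair | Criterion 3 causality met? | Criterion 4 causality met? |
|---|---|---|
| Possibly + Possibly | yes | no |
| Possibly + Probably | yes | yes |
| Probably + Probably | yes | yes |
| Probably + Definitely | no | yes, through the Probably event |
| Possibly + Definitely | no | no |
| Definitely + Definitely | no | no |

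Criterion 3 fails in 3 of the 6 pairs, and in 2 of those 3 criterion 4 fails as well. With the wording proposed under the fix, all 6 meet criterion 3's causality condition. These are counts of wording combinations, not probabilities.

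**Step 4. Criterion 4 on its own.** It has no grade or participant-count threshold. A single non-serious, medically relevant effect rated Definitely also falls outside it.

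**Step 5. Where the gap sits.** Group 2's share of enrolment is 132 / 141 = 0.936, about 94%. This is the share of participants treated after the only scheduled SRC meeting. It does not estimate how often the gap would matter.

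**The case against.** The best reply is that nobody would apply the rule this way. The SRC includes the enrolling investigators, an independent medical monitor and the sponsor's medical representative, and it would have to treat a definite relation as less worrying than a probable one. Table 6 has a similar looseness: its Unrelated row refers to the criteria for the levels from unlikely to probable and also leaves out definite. That suggests inherited wording, not an intended exclusion.

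The SRC's powers are also wider than the list. Section 6.3 lets it stop the trial without tying that power to the four criteria, and it receives blinded safety data during the study. Safety is reviewed on an ongoing basis in Group 2, and ad-hoc meetings are allowed. The events left over are few: related SAEs fall under criterion 1, and many events of Grade III or above would be serious. The pair count depends on convention: with ordered pairs it is 5 of 9 failing criterion 3 and 3 of 9 failing both. The SRC Charter, which is not among the documents, may already use the full scale.

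Most of this stands, and it limits the practical effect. It does not make the text correct. What is missing is the written trigger for a review and a hold, not the ability to stop, and relying on each reader to supply the missing word is a reason to add it.

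**Conclusion.** The point holds. Criteria 3 and 4 of section 6.3 are wrong as written, because they exclude the top level of the protocol's causality scale and conflict with criterion 1, section 12.1 and SAP section 14.1. On a literal reading, non-serious Grade III events of the same type, outside Hy's law and rated Definitely in two participants, meet none of the four criteria.

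The practical effect is small, and a drafting slip is the likely cause. Serious events and Hy's law cases are not affected. The conclusion rests on the protocol wording alone; the charter could narrow the gap in practice but would not correct the protocol. The correction should be made because the error sits in the participant-safety rules and costs very little to remove.

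**What to change.** In section 6.3:

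- Criterion 3: change the causality wording to at least possibly related (possibly, probably or definitely).
- Criterion 4: change it to at least probably related (probably or definitely).
- In both, refer to the scale in section 12.2.2.

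Check the SRC Charter and align it if it repeats the current wording.

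The cost is a few words in two bullets plus the amendment step in section 18.3. If the sponsor classes the change as a clarification of wording, it goes to the ethics committee for information only. If it is classed as substantial, it needs approval before use. Sample size, endpoints and analysis do not change.
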